13.3. Reporting of related Serious Adverse Events to the Sponsor and REC

The Chief Investigator will be responsible for the prompt notification of findings that could adversely affect the health of patients or impact on the conduct of the trial. Notification of confirmed unexpected and related SAEs will be to the Sponsor and the REC within 15 working days of the Chief Investigator becoming aware of the event, using the HRA report of serious adverse event form (see HRA website). Events that are classified as probable and possible will be treated as related for the purposes of AE reporting.

13.4. Events exempt from immediate reporting as SAEs

The following events are recognised complications of TAVI surgery and CEP use. They do not need to be reported separately as adverse events, but should be reported as part of the CRF.

13.4.1. TAVI

- 1) Acute Coronary Syndrome ACS
- 2) Acute Kidney Injury
- 3) Angina
- 4) Aortic dissection
- 5) Aortic rupture
- 6) Arrhythmia
- 7) Arteriovenous fistula
- 8) Atelectasis
- 9) Bleeding, operative or post-operative
- 10) Cardiac Arrest
- 11) Cardiac Tamponade
- 12) Cardiogenic Shock
- 13) Complications of suicide ventricle
- 14) Conduction system injury (with or without temporary or permanent pacing)
- 15) Congestive Heart Failure (CHF)
- 16) Death
- 17) Delirium
- 18) Endocarditis
- 19) Embolism, including air
- 20) Gastrointestinal (GI) bleed
- 21) Hematoma
- 22) Ischemia (coronary, limb, carotid)
- 23) Infection (local or systemic)
- 24) Myocardial Infarction (MI)
- 25) Nerve injury
- 26) Pain at access site
- 27) Paravalvular leak
- 28) Pericardial effusion
- 29) Pulmonary oedema
- 30) Pulmonary embolism

- 31) Right Ventricular Failure (RVF)
- 32) Severe LV dysfunction
- 33) Stroke
- 34) Vascular injury (e.g., dissection, rupture, perforation, pseudoaneurysm)

13.4.2. CEP

- 1) Complications at the site where the device is introduced (this will either be an artery at the wrist or elbow), such as bleeding, blood vessel injury (e.g. dissection, rupture, perforation, pseudoaneurysm), nerve injury, haematoma (large bruise)
- 2) Aortic, brachiocephalic or carotid artery dissection
- 3) Kidney injury (due to the need for additional administration of radiographic contrast medium)

13.5. Reporting procedures for Non-Serious Adverse Events

- Events which are expected complications of TAVI surgery and CEP use do not need to be reported separately as adverse events, but should be reported as part of the CRF (see section 13.4)
 - Post-discharge, recognised complications of TAVI surgery and CEP use do not need to be reported.
- Site study team will report unexpected Non-Serious Adverse Events (NSAEs) that are possibly or probably related to clinical trial activities as defined in section 13.1) using the secure, password protected trial database within 14 days of the site study team becoming aware of the event.
- NSAEs are reported up to the 6-8-week follow-up timepoint.
- The site study team will provide additional, missing or follow up information in a timely fashion if requested.
- The Chief Investigator will review reported AEs for causality as defined in section 13.1.

14. STATISTICS

Statistical analysis will be coordinated from the Clinical Trials Unit at London School of Hygiene and Tropical Medicine.

14.1. Statistical analysis and methods

A detailed statistical analysis plan (SAP) will be produced prior to unblinding of any data. In summary, the primary analysis will be a comparison of the incidence of stroke at 72-hours after TAVI between patients randomised to receive CEP and patients randomised to TAVI without CEP (standard care). A risk ratio and 95% confidence interval (CI) will be calculated together with a p-value. The event rate is expected to be low and the absolute impact of CEP will also be assessed with a risk difference and 95% CI. The primary analysis will be on an intention to treat basis. Secondary clinical outcomes will be analysed using the above approach. In addition, a multivariable logistic regression model will be developed to identify those patients at higher underlying risk of a stroke at 72 hours. Details will be provided in the SAP but briefly independent risk factors will be identified and a patient's individual risk for a stroke will be calculated. In order to assess the effect of CEP by risk, patients will be categorised according to their underlying risk of a stroke. The percentage of patients with stroke will be tabulated by treatment group and risk category along with absolute risk differences, to consider whether the impact of CEP depends on underlying risk.

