7.2. Key Secondary outcomes

- **1.Combined incidence of all-cause mortality or non-fatal stroke** at 72 hours post-TAVI or hospital discharge (if sooner). Stroke will be assessed as defined in section 7.1.2.
- **2.** Combined incidence of all-cause mortality, non-fatal stroke or transient ischaemic attack at 72 hours post-TAVI or hospital discharge (if sooner).
- 3. Incidence of all-cause mortality: at 72 hours post-TAVI or hospital discharge (if sooner)
- **4**. **Win ratio for all-cause mortality, disabling stroke and non-disabling stroke** at 72 hours post-TAVI, or hospital discharge (if sooner)
- 5.Incidence of all-cause mortality: at 12 months post-TAVI.
- **6. Incidence of all-cause mortality:** up to the end of the trial. This will use trial data up to 12 months, and centrally held NHS data from 12 months to the end of the trial
- **7.** Incidence of stroke as defined by centrally held NHS data (described in section 14.7): Identified between 72 hours post-TAVI or hospital discharge (if sooner) and 30-days post-TAVI.
- **8.** Incidence of stroke as defined by centrally held NHS data (described in section 14.7): Identified between 30-days post-TAVI and the end of the trial.
- **9. Stroke Severity:** In participants who had a stroke within 72-hours post-TAVI or hospital discharge (if sooner) will be assessed using the National Institutes of Health Stroke Scale (NIHSS). This measure has been adopted as a secondary outcome to explore the association between use of the CEP and prevention of large cerebral vessel occlusion (LVO). Strokes with an NIHSS score of 10 or greater will be defined as severe.
- **10. Disability Outcome:** Stroke recovery and/or ongoing disability in participants who had a stroke within 72-hours post-TAVI or hospital discharge (if sooner) will be assessed with the smRSq at discharge and between 6-8 weeks post-TAVI and at 12-months post-TAVI.

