10.11. Definition of End of Trial

The end of the trial is the date of the last completed 12-month follow-up visit (Visit 2 in section 10.8.3)

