To assess long-term stroke and mortality outcomes, we will link trial participants recruited at NHS sites to Hospital Episode Statistics (HES) and mortality data held by NHS England other central UK NHS bodies and the Office for National Statistics (ONS). Participant's NHS number and their date of birth or their Community Health Index will be shared securely between the London School of Hygiene & Tropical Medicine/University of Oxford and NHS England/other central UK NHS bodies /Office for National statistics (ONS) via secure email in order to request the health outcome data of participants. NHS England/other central UK NHS bodies /ONS will return the requested information to the London School of Hygiene & Tropical Medicine/University of Oxford in pseudo-anonymised form which is only identifiable to the data controller. The data will be held in a secure database on the server at the London School of Hygiene and Tropical medicine. Researchers at the University of York and The Newcastle upon Tyne Hospitals NHS Foundation Trust will be given access to the secure server to undertake analyses for the trial.

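### Mortality and stroke to the end of the trial (outcomes 6 and 8) fall under a risk ratio and risk difference rule although planned follow-up runs from 12 to about 70 months

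*Protocol*

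**What the plan says.** Section 14.1 sets out the primary analysis: "A risk ratio and 95% confidence interval (CI) will be calculated together with a p-value", and "the absolute impact of CEP will also be assessed with a risk difference and 95% CI". It then extends this to the rest: "Secondary clinical outcomes will be analysed using the above approach". The section is offered as a summary, with the promise that "A detailed statistical analysis plan (SAP) will be produced prior to unblinding of any data".

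Section 7.2 contains two secondary outcomes without a fixed horizon. Outcome 6 counts deaths from any cause until the trial closes: "This will use trial data up to 12 months, and centrally held NHS data from 12 months to the end of the trial". Outcome 8 is stroke from centrally held NHS data: "Identified between 30-days post-TAVI and the end of the trial". Section 10.11 makes the closing point a single calendar date: "The end of the trial is the date of the last completed 12-month follow-up visit". The synopsis gives a 58-month recruitment period and 12 months of individual involvement.

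On data sources, section 14.7 says "we will link trial participants recruited at NHS sites to Hospital Episode Statistics (HES) and mortality data held by NHS England". Section 21.2 (Insurance) refers to patients recruited at private hospitals, without giving their number.

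For outcomes 6 and 8 the protocol names no hazard ratio, Kaplan-Meier estimate, person-time, censoring rule or competing event.

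**The concern.** A risk ratio and risk difference suit outcomes with a common window: 72 hours, day 30, or 12 months. For outcomes 6 and 8 the window is set by the recruitment date. The first participant can be observed for nearly six years and the last for one. The proportion with an event is then an average of risks over unlike periods, and the average changes if recruitment was faster early or late. A reader cannot attach the reported incidence or absolute difference to a time horizon. It also cannot be compared with another study or carried into a lifetime cost-effectiveness model as a risk at a stated time.

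There is also a coverage gap. Participants recruited outside NHS sites are not covered by the linkage. On the protocol's text, outcome 6 has no data for them after 12 months and outcome 8 has no data source for them at all. A simple proportion needs everyone in its denominator to have a known status at the end; a time-to-event analysis does not.

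**Working it through.** **The plan's own figures.** The protocol gives no event rate, power or sample size for outcomes 6 and 8, so there is nothing of theirs to reproduce. Its primary-outcome calculation (3% against 2%, 80% power, 5% two-sided) reproduces at 2 × 3826 = 7652, or 7730 after 1% losses. This point does not affect it.

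**Length of follow-up.** Inputs: 58 months of recruitment and 12 months of involvement (synopsis), closing at the last 12-month visit (10.11).
- Last participant: 12 months. First participant: 58 + 12 = 70 months.
- Mean under uniform accrual: 12 + 58/2 = 41 months.
- Outcome 8 starts at day 30, so its window is about 11 to 69 months.

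**What the crude proportion estimates.** Assumptions (the protocol gives no long-term rates): constant mortality of 10% a year in the control arm, so λ = −ln(0.90)/12 = 0.00878 per month; constant hazard ratio HR; no losses.
- Risk by a fixed time t: 1 − exp(−λ·HR·t).
- Crude proportion, follow-up uniform on 12 to 70 months: 1 − [exp(−12λHR) − exp(−70λHR)]/(58λHR).
- Control: 1 − (0.9000 − 0.5409)/0.5092 = 29.5%.
- CEP, HR 0.80: 1 − (0.9192 − 0.6116)/0.4074 = 24.5%.

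| | Risk difference, HR 0.80 | Risk ratio, HR 0.80 | Risk difference, HR 0.90 | Risk ratio, HR 0.90 |
|---|---|---|---|---|
| 12 months | 1.9 points | 0.81 | 1.0 points | 0.90 |
| 36 months | 4.8 | 0.82 | 2.3 | 0.91 |
| 70 months | 7.1 | 0.85 | 3.4 | 0.93 |
| Crude, 12 to 70 months | 5.0 | 0.83 | 2.4 | 0.92 |

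With assumed annual mortality of 5% to 15% and HR 0.80, the crude control proportion runs from 15.9% to 41.1%, the crude difference from 2.9 to 6.3 points and the crude ratio from 0.82 to 0.85.

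**Dependence on accrual.** Same 10% mortality; only the recruitment curve changes. Front-loaded means a rate falling linearly to zero over 58 months; back-loaded is the reverse.

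| Accrual | Mean follow-up | Crude control mortality | Difference, HR 0.80 | Difference, HR 0.90 |
|---|---|---|---|---|
| Front-loaded | 50.7 months | 35.4% | 5.8 points | 2.8 points |
| Uniform | 41.0 | 29.5% | 5.0 | 2.4 |
| Back-loaded | 31.3 | 23.5% | 4.1 | 2.0 |

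With HR 1 the difference is zero for every curve. The crude ratio moves only between 0.82 and 0.84 at HR 0.80.

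**Competing death, outcome 8.** With equal stroke hazards in both arms (assumed 1% to 3% a year), the crude stroke risk ratio is 1.00 if mortality is equal, about 1.02 if the death hazard ratio is 0.90 and about 1.04 if it is 0.80.

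**The case against.** The best defence is that 14.1 is a summary and defers to an SAP, which was not available here. Its sentence cannot be literal for every outcome: a risk ratio cannot analyse the win ratio, the NIHSS score or the MoCA. It is shorthand for binary outcomes, and the choice of a survival method is often left to the SAP. That lowers the weight of the point but does not remove it. Outcomes 6 and 8 are worded as incidences, so the shorthand reaches them naturally, and it states a method rather than leaving one open. An SAP using time-to-event methods would depart from the protocol's wording.

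The illustration can also be challenged. Section 7.1.1 says CEP acts only on procedure-related embolic stroke, and the design expects to prevent strokes in 1 point of patients. A mortality hazard ratio of 0.80 sustained for 70 months exceeds that already at 12 months (1.9 points). This stands: the size of the shift in the risk difference is hypothetical. If any effect were confined to early deaths, the difference would vary far less with the horizon, and what would chiefly lack a time would be the incidence in each arm.

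Four stronger readings are tempting, and the documents do not support them.
- That the comparison is biased or its test invalid. Allocation is 1:1 in permuted blocks within centre, so follow-up should balance between arms, and the expected difference under no effect is zero for any recruitment curve.
- That unequal follow-up pulls the ratio towards 1. A risk ratio is nearer 1 than the hazard ratio at any fixed horizon too; the crude 0.83 lies between 0.81 at 12 months and 0.85 at 70.
- That a crude stroke proportion ignores death. It does not treat death as censoring; it estimates cumulative incidence averaged over follow-up.
- That unlinked participants will be counted as event-free. The protocol says this nowhere, and 14.5 promises appropriate handling of missing values. Leaving them out of outcome 8 is at least as natural a reading.

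**Conclusion.** The point holds as one about what the estimates mean for two secondary outcomes. Section 14.1 fixes a risk ratio and risk difference, and outcomes 6 and 8 have planned follow-up of 12 to about 70 months, so the resulting incidence and absolute difference belong to no stated time and depend on accrual as well as on CEP. The follow-up range comes from the protocol's own figures, as planned; withdrawals can shorten it. The effect sizes are assumptions: at 10% annual mortality, accrual shape alone moves crude control mortality between 23.5% and 35.4%, and with HR 0.80 the difference between 4.1 and 5.8 points.

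The validity of the test under no effect, the direction of the comparison and, to within a few hundredths, the risk ratio are not in question. The primary outcome, the 72-hour outcomes, stroke to 30 days and 12-month mortality have fixed horizons and are unaffected by unequal follow-up. The linkage gap is real on the protocol's text, but its size is unknown because the number of participants from private hospitals is not given.

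**What to change.** In section 14.1, limit the risk ratio and risk difference sentence to outcomes with a fixed window, and add:
- Outcome 6: time to death from any cause, with Kaplan-Meier curves and a hazard ratio with 95% CI.
- Outcome 8: cumulative incidence of stroke from day 30 with death as a competing event, plus a hazard ratio with 95% CI.
- Absolute differences between arms at pre-specified times within the range of follow-up, for example 1 and 3 years.
- Participants without linkage: censor at the last covered date for outcome 6; restrict outcome 8 to linked participants and report how many are left out in each arm.

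The SAP should carry the same text. The cost is a wording change and a small amount of standard extra analysis. No new contact with participants is needed, but dates of death and stroke must be obtained with the linked records, so the data request should ask for them.

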14.2. Sample Size Determination

If the proportion experiencing the primary outcome is 3% in the control arm, we will require 7652 patients to detect a 33% relative risk reduction (risk ratio 0.67) to 2%. Assuming 1% losses/withdrawals we will recruit 7730, for 80% power and 5% significance. For the secondary combined outcome of all-cause mortality or stroke at 72 hours, a trial of 7730 would also provide very good power. For example, for a 33% relative reduction from a combined rate of 4.2% a trial of 7730 would provide power well in excess of 90%.

The event rate for the primary outcome is based on a review of published data from randomised trials and registries. Self-reported stroke rates in registries are less than those reported in randomised trials, where there is more active stroke ascertainment. A recently published patient level analysis reported a 72-hour stroke rate of 5.4% in the control group, and the recently published meta-analysis shows stroke rates of 6%. In the UK registry the self-reported incidence was 2.6% in 2017. We believe that by using a structured approach using the QVSFS the stroke ascertainment rate is likely to be higher. We have been conservative in our predicted event rate for all stroke at 3%, which is still nearly half of that reported in previous randomised TAVI trials.

Previous published studies suggest a potentially large impact of CEP on reducing incidence of stroke. However, these are not based on well-powered randomised trials and may overestimate efficacy. Therefore, the proposed effect size is based on more conservative estimates in comparison to data published from observational studies or small-randomised trials, while still representing a clinically meaningful reduction in stroke.

14.2.1. Sample size increase

To maximise the chance of delivering a definite result for the trial, the sample size was increased from 7730 to 9712.

14.3. Analysis Populations

The primary analysis of the trial will be on an intention to treat basis, including all participants whose TAVI procedure is started according to the group to which they were randomised irrespective of whether they received the intervention as allocated. In addition, a per protocol analysis and complier average causal effect analysis will also be performed. Full details will be included in the separate Statistical Analysis Plan.

14.4. Stopping criteria

The following decision points and interim analyses are built into the trial design:

Milestone 1: Feasibility of recruitment 24 months after trial commences: We will assess feasibility 24 months after the trial commences using the following criteria:

- 1. Completed set up of at least 20 sites
- 2. Randomised at least 80 participants per month over the preceding 3 months
- 3. Randomised at least 800 participants in total

If these targets are not met, then the Trial Steering Committee and BHF will consider the feasibility of continuing the trial.

Milestone 2: The first interim analysis will be after 50% of patients (3865 patients) have completed follow-up for the primary event.

Milestone 3: The second interim analysis will be after 70% of patients (5411 patients) have completed follow-up for the primary event.

Milestone 4: Due to the increase in the sample size, a third interim analysis will take place once 134 primary outcome events have occurred.

Interim analysis (Early stopping criteria for efficacy or futility): The Data Monitoring Committee (DMC) will be convened to monitor the safety of patients and perform interim analyses at Milestones 2, 3 and 4 to assess futility and efficacy. Interim analyses may lead to the early closure of the trial following consultation with the Trial Steering Committee (TSC), Sponsor and Funder. Other outcome and safety data would be considered by the DMC in making their recommendation.

The Level of Statistical Significance

The trial is designed to assess the primary outcome with 80% power and 5% significance.

14.5. Procedure for Accounting for Missing, Unused, and Spurious Data.

All patients randomised to the trial will be analysed on an intention-to-treat basis. Data will be validated through data review and querying, and the data analysis will take appropriate account of missing values. This process will be detailed in the statistical analysis plan.

14.6. Health Economics Analysis

A cost-effectiveness model will be developed to estimate the short-term (1-year) and longer-term (lifetime) survival and quality-adjusted life years (QALYs) and the costs incurred by the NHS and Personal Social Services (PSS). The analysis will also address whether value for money could be further optimised within the overall TAVI population (e.g. using additional risk stratification). In addition to the primary and secondary trial endpoints, we will prospectively link the trial participants to collect further data until the end of their participation in the trial on subsequent stroke and other events (from Hospital Episode Statistics [HES], hospital resource utilisation [HES] and mortality (Office for National Statistics [ONS]). The linkages to HES and ONS will provide a more complete picture of the short and longer-term costs and outcomes and will enhance the precision and robustness of the cost-effectiveness results. Resource utilisation during the initial index admission will be collected. This will include information on the duration of the procedure, any additional procedures and consumables and the duration of the initial index admission (including any periods in ICU). To estimate healthcare costs, we will assign national average costs using NHS Reference costs and PSSRU (Personal Social Services Research Unit) unit cost estimates. We will collect quality of life measures using the standardised EQ-5D-5L at baseline and at 12 months to estimate QALY changes over the 12-month follow-up. The longer-term model will extend the time horizon to a lifetime. The model will take into account uncertainty in the evidence base (including risk of events, outcomes and costs). Our results will determine the probability of CEP being cost-effective, conditional on various levels of willingness-to-pay values for gain in health benefit. Sensitivity analyses will be conducted to evaluate the impact of alternative model assumptions.

14.7. Use of centrally held data to assess long-term stroke and mortality follow-up in patients recruited at NHS sites.

To assess long-term stroke and mortality outcomes, we will link trial participants recruited at NHS sites to Hospital Episode Statistics (HES) and mortality data held by NHS England other central UK NHS bodies and the Office for National Statistics (ONS). Participant's NHS number and their date of birth or their Community Health Index will be shared securely between the London School of Hygiene & Tropical Medicine/University of Oxford and NHS England/other central UK NHS bodies /Office for National statistics (ONS) via secure email in order to request the health outcome data of participants. NHS England/other central UK NHS bodies /ONS will return the requested information to the London School of Hygiene & Tropical Medicine/University of Oxford in pseudo-anonymised form which is only identifiable to the data controller. The data will be held in a secure database on the server at the London School of Hygiene and Tropical medicine. Researchers at the University of York and The Newcastle upon Tyne Hospitals NHS Foundation Trust will be given access to the secure server to undertake analyses for the trial.

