7.1.1. Incidence of all stroke at 72-hours after TAVI

The primary outcome is stroke at 72-hours (or at hospital discharge, if sooner) as this is the main clinical outcome that CEP might influence. From a mechanistic perspective, CEP will only impact on procedure-related embolic stroke.

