10.7. Baseline assessments

Visit T-2 Initial patient approach at pre-procedure visit (done by clinical care team)

- Eligibility assessment (prior to visit)
- Patient information sheet provided if patient eligible
- Patient invited to join study

Visit T-1 Informed consent and baseline data collection (during clinical visit or study visit either in person or over the telephone/videoconference)

Baseline data can be collected at any time from consent up to the time of the patient's TAVI procedure.

- Informed consent collected
- Demographics
- Medical history
- Upload standard of care imaging (CT and echo)
- Concomitant medications
- smRSa
 - Short questionnaire administered for the study
- EQ-5D-5L
 - Short questionnaire administered for the study

TAVI Procedure

- Randomisation (this will be done by the cardiologist or other delegated staff member)
- The start of the TAVI procedure is defined as first arterial puncture.
- TAVI with CEP (intervention arm)
 - The TAVI procedure takes approximately 90 minutes and is done by a cardiologist. The
 CEP adds approximately 5 minutes to the procedure and is done by the cardiologist.
- TAVI without CEP (standard of care) (control arm)
 - The TAVI procedure takes approximately 90 minutes and is done by a cardiologist.

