10.8.2. Visit 1 – 6-8 weeks post-TAVI

This will be conducted by telephone for the study, however if there is a pre-scheduled clinical visit, it can be done in person.

Contact with the patient will be arranged by a delegated member of the research team at the local hospital. Phone calls are projected to take no more than 10 minutes to complete the EQ-5D-5L questionnaire. The staff contacting the patient will check electronic records prior to contacting the patient to ensure they have not died. While participant preferences for contact will take priority, we advise that after 3 unsuccessful attempts to reach the patient no further attempts are made.

Secondary outcomes assessed:

- Mortality status
 - Taken from patient notes
- smRSq
 - Short questionnaire administered for the study (only done in presence of a stroke outcome)
- EQ-5D-5L
 - Short questionnaire administered for the study
- Vascular injury
 - Taken from patient notes
- Safety reporting
 - Taken from patient notes

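### Section 14.6 bases 12-month QALYs on EQ-5D-5L at baseline and 12 months, although the schedule also collects it at 6-8 weeks, the measurement closest to a procedural stroke

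*Protocol*

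**What the plan says.** Section 14.6 (Health Economics Analysis) describes a model to "estimate the short-term (1-year) and longer-term (lifetime) survival and quality-adjusted life years (QALYs") together with NHS and social-services costs. For quality of life it names "quality of life measures using the standardised EQ-5D-5L at baseline and at 12 months to estimate QALY changes over the 12-month follow-up". It mentions no other time point and no interpolation rule.

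The schedule differs. The procedures table in 10.6 marks EQ-5D-5L at baseline, 6-8 weeks and 12 months. Section 10.8.2 lists it at Visit 1 without the stroke-only condition attached to the smRSq, and describes the call in terms of that questionnaire: "Phone calls are projected to take no more than 10 minutes to complete the EQ-5D-5L questionnaire". Item 13 of section 7.2 assigns the EQ-5D-5L to the cost-effectiveness analysis without giving time points. Nothing in the protocol gives the 6-8 week value a different purpose.

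**The concern.** The effect under test falls at the very start of the 12-month window. Section 7.1.1 states: "From a mechanistic perspective, CEP will only impact on procedure-related embolic stroke". The primary outcome closes at 72 hours or discharge. The baseline questionnaire precedes the procedure (section 10.7: "Baseline data can be collected at any time from consent up to the time of the patient's TAVI procedure"), so it cannot reflect a procedural stroke. If 14.6 is followed as written, the first utility recorded after the stroke that enters the QALY estimate is the one at 12 months.

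A line drawn from baseline to 12 months would credit a stroke patient with near-baseline utility in the first weeks and would hide any dip that later recovers. Cost-effectiveness at 12 months is a listed secondary outcome, and the stroke-related part of its QALY difference would generally come out too small.

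This is more than detail left for a later plan. Section 14.6 names the time points itself and, unlike 14.1, 14.3 and 14.5, does not refer onward to the statistical analysis plan.

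**Working it through.** The protocol gives no QALY figure, utility or interpolation rule, so there is nothing to reproduce. The check asks what linear interpolation would do with two points and with three.

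**Inputs from the protocol.** EQ-5D-5L times: baseline, 6-8 weeks, 12 months (10.6, 10.8.2, 10.8.3). Design stroke rates: 3% in control and 2% with CEP (14.2), a difference of 0.01.

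**Assumptions.** d7 is the utility decrement of a stroke patient against a stroke-free patient at 6-8 weeks, and d12 the decrement at 12 months. The decrement at baseline is 0, because baseline precedes the procedure. The middle visit is placed at 7 weeks, so t = 7/52 = 0.135.

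**Formulas (trapezium rule), QALY loss per stroke over one year.**

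- Two points: 0.5 × d12
- Three points: 0.5 × d7 × t + 0.5 × (d7 + d12) × (1 − t) = 0.5 × d7 + 0.5 × d12 × (1 − t)
- Share captured by two points: r / (1 + r(1 − t)), with r = d12/d7

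**Results with d7 = 0.30.**

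| d12 | Two points | Three points | Share captured |
|---|---|---|---|
| 0.30 (no recovery) | 0.150 | 0.280 | 54% |
| 0.20 | 0.100 | 0.237 | 42% |
| 0.15 | 0.075 | 0.215 | 35% |
| 0.10 | 0.050 | 0.193 | 26% |
| 0 (full recovery) | 0 | 0.150 | 0% |

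The share depends only on r, so d7 = 0.20 or 0.50 gives the same percentages at the same r. Placing the visit at 6 or 8 weeks moves the share by at most about 1 point.

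**Later worsening.** With d7 = 0.20 and d12 = 0.40, two points give 0.200 and three give 0.100 + 0.5 × 0.40 × 45/52 = 0.273. The share is 73%, a factor of 1.4. The share would pass 100% only if r exceeded 1/t = 52/7 = 7.4, which is why the direction is general rather than certain.

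**Full utility paths (assumed), at 0/7/52 weeks.**

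- No stroke, 0.70/0.80/0.80: two points (0.70 + 0.80)/2 = 0.750; three points 0.75 × 7/52 + 0.80 × 45/52 = 0.793.
- Stroke, 0.70/0.40/0.55: two points 0.625; three points 0.55 × 7/52 + 0.475 × 45/52 = 0.485.
- Loss per stroke: 0.750 − 0.625 = 0.125 against 0.793 − 0.485 = 0.308, a factor of 2.5.

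**Per randomised patient at the design difference of 0.01.** With d7 = 0.30 and d12 = 0.15, the stroke-related gain is 0.01 × 0.075 = 0.00075 QALY (two points) against 0.01 × 0.215 = 0.00215 (three points), a factor of 2.9. With the full paths above it is 0.00125 against 0.00308.

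**The case against.** Five points can be made in favour of the plan.

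- **The text does not exclude the third point.** Section 14.6 is worded as a statement of what is collected. A reader might infer that QALYs will use two points alone, joined by a straight line, but the protocol says neither. This stands: the bias above is conditional on interpolation between the named points. The disagreement with the schedule is not conditional.
- **The QALYs come from a model.** A model can attach a utility loss to each stroke and death instead of joining questionnaires. This stands as a limit on the consequence, although the protocol does not say that the model will do so.
- **Much of the benefit lies elsewhere.** A reader might infer that nearly all of the device's QALY benefit is early stroke loss, so that the whole cost-effectiveness result is off by a factor of two or more. The protocol does not support that. Section 6.1 links TAVI stroke to lost independence and early death, 6.5 stresses lifetime consequences, and 14.6 includes survival and a lifetime horizon. The calculation concerns one component, first-year utility.
- **The stroke-free shortfall is not a second bias.** In the illustration, stroke-free patients lose 0.793 − 0.750 = 0.043 under two points. At design rates this applies to 97% and 98% of the two arms, so it largely cancels in the difference, and what remains is already inside the 0.125 against 0.308 contrast.
- **The third point has a cost.** Visit 1 is usually by telephone, with advice to stop after three failed attempts. If stroke survivors are harder to reach, the added values may be informatively missing. This stands, but it is a reason to plan for missing values rather than to leave the measurement out.

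**Conclusion.** The point holds as an inconsistency with a conditional consequence. Section 14.6 names two time points where the schedule has three, and the one left out is the closest to the event under study. That rests on the text alone.

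The size rests on assumed utilities and on linear interpolation. Two points would then capture 0% to about 54% of the three-point first-year loss per stroke when the decrement stays level or recovers after 6-8 weeks, and more if it grows. The first-year stroke-related QALY difference would generally be understated. The amounts per randomised patient are small, around 0.001 against 0.002 to 0.003 QALY, but they are the stroke-related first-year utility gain at the design difference.

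The documents do not support any particular factor for the overall cost-effectiveness result. The change is worth making for a named secondary outcome; it has no bearing on the primary analysis.

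**What to change.** Amend 14.6 to state that EQ-5D-5L is collected at baseline, 6-8 weeks and 12 months, and that 12-month QALYs are the area under the utility curve through all three. Handling of deaths, adjustment for baseline utility and treatment of missing 6-8 week values can be left to the analysis plan. The change takes one sentence and no new data collection; the only real cost is dealing with missing questionnaires at the telephone visit.
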